11. DATA COLLECTION AND QUALITY ASSURANCE

11.1 Data Collection Forms

Consented patients' data (including screening questions, demographics (age in years, race, sex (m/f) and BMI (continuous)), and the survey on mouth rinse acceptability) will be collected using the CDART dental toolkit program, which stores data on a secure UNC maintained server and meets federal guidelines for clinical study data acquisition. The CDART electronic forms and database will serve as our CRFs and source data. IRB approved study personnel will ask participants the questions and will enter responses into this encrypted, password protected database. Data will be collected in this program using participant's study ID and no other personal health identifiers (PHI). A separate linkage file, securely stored on UNC servers, will be utilized to associate the random alphanumeric study ID with patient identifier, so samples and data will not be associated with patient identifiers. Data will only be transmitted among the research team using the school of dentistry secure research servers. Demographic data will be transmitted among the research team through access to the secure CDART research database system, stored on secure UNC servers, which study personnel will access only through encrypted computers via secure user accounts.

11.2 Data Management

An Excel key will be created with study ID (random alphanumeric code) to identify patients, saved in a secure folder on a UNC SOD server. This linkage file will be stored separately from data and destroyed at the close of the study. All data collected from participants and results from sample

analysis will be coded with unique numerical identifiers and stored in the UNC CDART clinical research database and on a secure UNC-CH server. Only trained, IRB-approved study personnel will enter and access data in the secure CDART research database.

Consented patients' data (including screening questions, demographics, and the survey on mouth rinse acceptability) will be collected using the CDART dental toolkit program, which stores data on a secure UNC maintained server and meets federal guidelines for clinical study data acquisition. Only HIPAA and human subjects trained IRB-approved study personnel will collect, enter and manage patient data; study coordinators will serve in this capacity.

Data will be collected in the CDART research database using participant's study ID and no other PHI identifiers, on approved, carefully designed digital forms within CDART. CDART forms will include questions with drop downs, radio button multiple choice and text field entry, depending on the question type. There will be separate digital forms for inclusion/exclusion screening questions (before sample collection begins), medical history, substance use history, demographic questions, and questions regarding mouthrinse experience (taste, color, sensation) and willingness to use a mouthrinse in various clinical settings (e.g. dentist or doctor appointments). A separate linkage file, securely stored on UNC servers, will be utilized to associate the random alphanumeric study ID with patient identifier, so samples and CDART data will not be associated with patient identifiers. Home diary entries will be made on paper or using a secure UNC Qualtrix account link, depending on patients' technological capabilities.

Data will only be transmitted among the research team using the SOD secure research server. Demographic data will be transmitted among the research team through access to the secure CDART research database system, stored on secure UNC servers, which study personnel will access only through encrypted computers via secure user accounts.

Linkage files containing identifiers will be deleted and permanently removed from all servers and study computers at the conclusion of the study with acceptance of associated manuscripts. Saliva specimens will be labeled with a study ID (random alphanumeric code) that is not identifiable without the linkage file, and therefore will not be identifiable after linkage file destruction.

10.3 Quality Assurance

11.3.1 Training

All study personnel have been trained in health privacy (HIPAA), human subjects research and good clinical practices through the CITI program and are certified to work with patient data on clinical trials. Study coordinators and healthcare providers are trained in and approved for the use of the CDART electronic research database and EPIC medical record system. Technical research personnel performing viral PCR and infectivity assays are approved to operate in their BL3 laboratory facilities and have specialized, lab-based training in these molecular techniques. They have also undergone training in the use of universal precautions and management of human biological samples along with bloodborne pathogen training. Finally, the GoHealth Clinical Research core has highly experienced research coordinators who will monitor all study staff to ensure protocol compliance and quality assurance.

11.3.2 Quality Control Committee

The investigators and study coordinators will meet weekly as an internal quality control committee to review consent documents, CDART data forms, and unanticipated problems with recruitment or adverse events. There is only one site for this study. The use of on-label, widely used mouthrinses and collection of saliva carry minimal risk for participants, apart from the very rare, undiagnosed allergy, which would be managed through proper referral to the neighboring UNC hospital. Therefore, there is no study quality control committee.

11.3.3 Metrics

Every salivary sample will be collected in a conical tube with millimeter markings to monitor salivary volume. If insufficient saliva is collected, the study personnel collecting the samples from participants will note insufficient volume in the CDART database for each applicable time point and will indicate in CDART if the subject must be withdrawn and replaced. If a patient is unable to generate sufficient saliva for the 0 min, 15 min or 30 min post-rinse time points, the subject will be removed from the study and this will be noted in CDART along with their insufficient samples. If a subject is unable to generate sufficient saliva for time points 45 or 60 min post-rinse, the participant will remain in the study but their insufficient samples will be noted in CDART. If a patient is unable to tolerate the blood draws or periodontal exam, this will be noted in CDART and the patient will be withdrawn from the study.

For RT-PCR, viral infectivity and multiplex Luminex assays, all salivary samples will be run in triplicate with standard experimental controls (negative and positive) and protocol quality checks performed by research technical personnel in the COVID Core, [name], [name] and [name] laboratories. SARS-CoV-2 viral infectivity and RNA level will be measured using an *in vitro* infectivity assay (Reduction factor [RF] calculated from PFU / mL) and RT-PCR (relative quantification [RQ] ratio). Cytokine and chemokine concentration (pg/mL) will be measured using a prevalidated multiplexed quantitative analyte assay on a bioanalyzer (Luminex technologies). This objective provides urgently needed data to guide healthcare workers on the proper use of specific commercially available mouthwashes capable of reducing SARS-CoV-2 viral infectivity and potentially limiting COVID-19+ transmission.

Outcome assessments will be conducted weeks to months after the study visit, when RT-PCR, viral infectivity and cytokine/chemokine assays are conducted in the COVID Core and the laboratory of [name].

The secondary objectives are to measure inflammation-associated cytokine and chemokine concentration (pg/mL) in saliva and blood samples taken from SARS-CoV-2+ participants and also to quantify the frequency of periodontal disease among study participants. The tertiary objectives of this study are a periodontal exam and to use post-rinse surveys to evaluate patient perceptions of the mouthrinse and feedback on their willingness to use the product (units: percentage of respondents). These tertiary outcomes are exploratory. Periodontal exams will be scored and reported according to the 2017 World Workshop on the Classification of Periodontal and Peri-Implant Diseases and Conditions, co-presented by the American Academy of Periodontology (AAP) and the European Federation of Periodontology (EFP).¹⁹

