3. STUDY DESIGN

One of the aims of this placebo-controlled, randomized, double-blinded study is to measure the efficacy of antiseptic mouthwashes on reducing SARS-CoV-2 cellular infectivity in COVID+ patient saliva (described above). Asymptomatic and symptomatic SARS-CoV-2+ subjects will be enrolled in the study (according to Inclusion and Exclusion Criteria - Section A.3). Symptomatic SARS-CoV-2+ subjects will be enrolled within 7 days of symptom onset. Subjects' samples are collected in the GoHealth Clinic (Adams School of Dentistry, UNC Chapel Hill, North Carolina, USA). Asymptomatic SARS-CoV-2+ subjects will be enrolled within one week of likely exposure. Study participants who meet all inclusion criteria without any exclusion criteria will be randomized to either an experimental or control group using block randomization.

Participants give a baseline salivary sample (2 mL over 5 min) and then asked to rinse with an mouth rinse for 30-60 sec (on-label instructions) according to the table below:

mouthrinse*	Number of final participants (sample size)	Group
1.5% w/v hydrogen peroxide rinse (Peroxyl)	25**	Experimental
0.12% Chlorhexidine Gluconate (Periogard)	25	Experimental

1 st Peroxyl; 2 nd Periogard [^]	25	Experimental
0.075% Cetylpyridinium Chloride (Colgate Total Zero)	25	Experimental
Sterile Water	25	Control

**All mouthrinses are commercially available in the USA, routinely used in clinical settings, and will be used in an on-label manner.*

***30 participants will be enrolled per regimen to ensure that complete data will be obtained from at least 25 participants per regimen. We assume that ≤ 5 enrollees will drop out or have incomplete data. 30 participants will be enrolled per arm to collect full data sets from 25 participants per arm, assuming some patients will need to be replaced due to inability to complete a visit (missing data).*

[^]For the sequential Peroxyl (1st) and Periogard (2nd) rinses, both oral rinses will be conducted in an on-label fashion. The patient will begin by rinsing with 10 mL of Peroxyl for 60 sec and then expectorate the mouthrinse into an empty tube. Then the patient will rinse with 15 mL of Periogard for 30 seconds and spit this mouthrinse into another empty tube.

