If a patient suffers from xerostomia/dry mouth, such that s/he cannot produce the baseline salivary sample volume or the immediate, 15 minute and 30 minute post-rinse saliva volumes, s/he will be removed from the study with a parking voucher, but without a visit 1 \$30 gift card and will be replaced. This would lead to missing data at the uncompleted time points. If a patient suffers from dry mouth, such that s/he cannot produce salivary sample volumes needed for later time points (45 min or 60 min post-rinse) but s/he produced sufficient baseline, immediate, 15 min and 30 min post-rinse samples, the participant will still be compensated with the visit 1 \$30 gift card and parking vouchers, and will remain in the study for visit 2 participation, if willing. At the conclusion of the visit 2 on site appointment (after saliva and blood samples have been collected and the periodontal exam is completed), participants will receive a \$50 gift card and parking vouchers. If a participant fails to carry out the at-home oral hygiene regimen with diary, cannot provide salivary or blood samples at visit 2, or cannot undergo the oral exam, they will not be provided the \$50 gift card for visit 2. Missing or deficient samples will be noted in CDART.

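### Sections 6.2.5, 9 and 11.3.3 do not state one removal rule, and an early missed saliva sample can cost the 30 min sample that the primary hypothesis needs

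*Combined protocol and SAP*

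**What the plan says.** **Early saliva.** Section 11.3.3 (Metrics) removes a patient who is "unable to generate sufficient saliva for the 0 min, 15 min or 30 min post-rinse time points, the subject will be removed". It does not name the pre-rinse baseline sample. Section 6.2.5 (Completion/Final Evaluation) removes and replaces a patient who "cannot produce the baseline salivary sample volume or the immediate, 15 minute and 30 minute post-rinse saliva volumes, s/he will be removed". Section 9 (Intervention Discontinuation) has the same rule.

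**Late saliva.** In 6.2.5 and 9, a participant who cannot give the 45 or 60 min sample "but s/he produced sufficient baseline, immediate, 15 min and 30 min post-rinse samples" stays in for visit 2. Section 11.3.3 agrees: for a subject "unable to generate sufficient saliva for time points 45 or 60 min post-rinse, the participant will remain in the study".

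**Blood and periodontal exam.** Under 11.3.3, a patient may be "unable to tolerate the blood draws or periodontal exam, this will be noted in CDART and the patient will be withdrawn from the study". No visit is named. Sections 6.2.5 and 9 speak of visit 2 only: if participants "cannot provide salivary or blood samples at visit 2, or cannot undergo the oral exam, they will not be provided the" visit 2 gift card, and the gap is noted in CDART. Both sections also let the investigator discontinue a subject at discretion, with insufficient saliva and inability to comply with procedures among the possible reasons.

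**Replacement and missing data.** Section 3 (Study Design) enrols 30 per arm for 25 full data sets, "assuming some patients will need to be replaced due to inability to complete a visit (missing data". It also says that missing data are left out of the analysis and are not expected to cause bias.

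**The concern.** Whether a given participant stays in depends on which section the coordinator follows. The clear case is blood and the periodontal exam. One section makes withdrawal mandatory. The other two mention a payment consequence and a database note, and otherwise leave the matter to discretion.

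The saliva rule has a second problem, which remains even if the sections are read as agreeing. Removal is triggered by a measurement taken after randomisation and after the rinse. It stops collection of the 30 min sample from someone who may be able to give it. Section 10.2 sets the hypothesis at a reduction lasting at least 30 minutes, and section 10.4 runs the infectivity assay on 0 and 30 min samples.

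If any rinse alters saliva flow, the loss could also differ by arm. The protocol's own adverse-effect tables list dry mouth and salivary-gland inflammation among reports for chlorhexidine, which is used in two of the five arms.

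**Working it through.** **1. The sections side by side**

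| Event | 11.3.3 | 6.2.5 and 9 |
|---|---|---|
| Baseline saliva insufficient | not named | removed, replaced |
| One of immediate, 15, 30 min insufficient | removed | literal *and*: not removed; with the retention clause: removed |
| Only 45 or 60 min insufficient | stays | stays |
| Blood or exam not done | withdrawn (visit not named) | visit 2: gift card lost, CDART note; status not stated |

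Take a participant who misses only the 15 min sample. Section 11.3.3 removes that person. The literal wording of 6.2.5 and 9 does not, yet their retention clause does not cover the case either, because it requires all four early samples.

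**2. What each removal costs**

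- *Immediate or 15 min saliva.* All later samples are lost, including 30 min. The pre-rinse sample has already been given, so a comparison of baseline with 30 min would still have been possible.
- *Visit 1 blood.* Section 3 and section 5.1 place it after the last saliva sample. The visit 1 saliva series is complete, and what is lost is visit 2, which serves secondary and tertiary outcomes.
- *Periodontal exam.* It is the last act of visit 2, so nothing later is lost.

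**3. The plan's own figure**

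Section 3 allows at most 5 losses in 30, or 5/30 = 16.7%. Then 25 / (1 − 5/30) = 30, which reproduces the enrolment per arm.

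**4. Illustration of the saliva rule**

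The documents give no chance *p* that a sample is insufficient. Assume *p* = 2%, 5% or 10%, independent between time points, and count removals among 30 enrolled with no other loss.

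- A: 11.3.3, any of three post-rinse samples: 1 − (1 − p)³. At 5%: 1 − 0.95³ = 0.143, × 30 = 4.3.
- B: 6.2.5 and 9 with the retention clause, any of four including baseline: 1 − (1 − p)⁴. At 5%: 1 − 0.95⁴ = 0.185, × 30 = 5.6.
- C: 6.2.5 and 9 literally, baseline or all three post-rinse: p + (1 − p)p³. At 5%: 0.05 + 0.95 × 0.000125 = 0.0501, × 30 = 1.5.

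Expected removals per 30, with the binomial probability that at least 25 remain:

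| Reading | p = 2% | p = 5% | p = 10% |
|---|---|---|---|
| A | 1.8 (0.99) | 4.3 (0.75) | 8.1 (0.14) |
| B | 2.3 (0.97) | 5.6 (0.51) | 10.3 (0.03) |
| C | 0.6 (1.00) | 1.5 (0.997) | 3.0 (0.92) |

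Low saliva output is likely to persist within a person, and severe dry mouth is already excluded. Correlated failures would narrow the gaps between the readings.

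**The case against.** The best defence is that the saliva rules hardly differ. Sections 6.2.5 and 9 keep someone who misses a late sample only if baseline, immediate, 15 and 30 min were all produced. This implies that any early miss leads to removal, as in 11.3.3. That stands: the saliva difference is mainly loose wording plus the baseline sample that 11.3.3 omits. It does not answer the second problem, because on that reading the 30 min sample is lost after a single earlier miss.

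Forfeiting a gift card is also a payment rule and does not say that the participant stays. That too stands. Retention after missed blood or exam is inferred from silence, and the firm contrast is mandatory withdrawal against discretion.

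Four stronger readings are tempting, and the documents do not support them:

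- *Blood or exam withdrawal stops primary data being collected.* It does not, given the order of procedures. Only the use of samples already given is in doubt. Section 6.2.5 describes removal as leaving gaps at the uncompleted time points, which suggests that completed samples are kept, but no section says so.
- *The literal rule in 6.2.5 and 9 removes almost nobody.* That leaves out baseline failure. Reading C gives 0.6 to 3.0 per 30.
- *The replacement rules contradict each other.* Section 3 speaks generally of an uncompleted visit, and early saliva failure is one instance. The other sections do not say that replacement is confined to saliva.
- *Removal is shown to bias the arms.* The adverse-effect tables give no frequency for dry mouth and no effect of a single rinse. This is a risk only.

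**Conclusion.** The point holds in a limited form. The three sections do not state one removal rule. The clear conflict is over blood and the periodontal exam; the saliva difference is mostly ambiguity. The consequence for the primary outcome comes from the saliva rule alone: removal after a missed immediate or 15 min sample means that the 30 min sample is not collected. Withdrawal over visit 1 blood costs visit 2 data, and withdrawal at the exam costs no later data.

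The size is not known. Over assumed failure rates of 2% to 10%, expected removals run from 0.6 to 10.3 per 30, depending on rate and reading, against an allowance of 5. These figures rest on independence and on no other losses. They show that the choice of wording could decide whether 25 complete series are reached, and they are not a forecast. The matter should be corrected before enrolment continues, mainly because the correction is cheap.

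**What to change.** Reconcile 6.2.5, 9 and 11.3.3, and the replacement wording in section 3, into one rule. It should name the baseline sample, say whether *any* or *all* applies, cover blood and the exam at each visit, and state who is replaced.

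For data collection, treat a missed post-rinse saliva sample, blood sample or exam as missing for that assessment only. Continue to collect the remaining samples from willing participants, including visit 2 saliva. State that all samples already given are analysed, and align the section 3 sentence that excludes missing data. The repeated-measures model planned in sections 10 and 10.6 can use incomplete series if it is fitted to all available observations; the plan should say that it will be. Because section 10 also names ANCOVA at each time point as primary, say which participants enter each of those models.

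Removal for safety, and decisions on continuing the home products, are outside this change.

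The cost is protocol wording. The downside is that some participants will have incomplete series, so the number analysed will vary by time point and should be reported by arm.

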11.3.4 Protocol Deviations

Protocol deviations will be recorded within source documentation (CDART) for each participant by study personnel during the study visits. The investigator and study coordinators will meet weekly to review unanticipated problems, adverse events and protocol deviations. All such events will be appropriately reported to the IRB board of UNC.

11.3.5 Monitoring

The quality control committee will meet weekly to review adverse events, protocol deviations, data quality in CDART, and collection of consent forms. The GoHealth Clinical Research core has highly experienced research coordinators who will monitor all study staff to ensure protocol compliance. A representative from the GoHealth core will participate in the weekly quality control committee meetings to review CDART records and consent forms.

12. PARTICIPANT RIGHTS AND CONFIDENTIALITY

12.1 Institutional Review Board (IRB) Review

This protocol and the informed consent document and any subsequent modifications will be reviewed and approved by the IRB or ethics committee responsible for oversight of the study. Consent forms are separate from this protocol document and were submitted as part of the IRB application.

12.2 Informed Consent Forms

Outpatients, who have tested positive for SARS-CoV-2 and consented to be contacted for study enrollment in the UNC Respiratory Diagnostic Center (RDC), will be contacted to participate in this study by research personnel. The subjects being approached by phone or email have signed a prior facility consent at the RDC confirming their willingness to share their name and contact information to be contacted for study participation in COVID-19 related research. We will not receive information on subjects that decline this internal consent. Patients will be contacted first by phone and, if not available, then by email. The study's purpose and requirements will be explained and the patient will have the opportunity to ask questions and will have time to consider participation. Interested patients will make an appointment to visit the Go Health Clinical Research Unit at Adams School of Dentistry for this study. Study participation includes two visits, one week apart. The consent forms will be reviewed and signed by interested patients in person in the Go Health Clinical Research Unit at Adams School of Dentistry.

A signed consent form will be obtained from each participant. For participants who cannot consent for themselves, such as those with a legal guardian (e.g., person with power of attorney), this individual must sign the consent form, though minors and patients who are intellectually delayed and unable to consent for themselves will be excluded. The consent form will describe the purpose of the study, the procedures to be followed, and the risks and benefits of participation. A copy will be given to each participant or legal guardian and this fact will be documented in the participant's record. For Spanish speaking patients and/or parents, Spanish forms will be provided and communication will occur through a Spanish translator. All patients are adults and over normal cognitive capacity, and therefore will be able to consent for themselves.

At the visit, a consented patient will answer screening questions regarding inclusion and exclusion criteria. Answers will be entered into the CDART research database managed by UNC. Prior to finalizing these screening questions, women participants of childbearing potential will be asked to provide a urine sample in the restroom, to undergo a rapid pregnancy test by study personnel. Any pregnant or lactating patients will be excluded.

Our study statistician, will create a block randomization schedule and perform these computations. All patients will be consented and then fill out our screening questions for inclusion and exclusion to confirm eligibility prior to being assigned to the randomization schedule.

